3. STUDY DESIGN

Study design: Single-center, single-blind, pilot randomized controlled trial

Primary outcomes:

- 1) Correlation between physiologic synchrony in patient-provider dyads (GSR or HRV) and improvement in GERD symptom severity.
- 2) Correlation between absolute changes in GSR within subjects over the course of the study visit and subsequent changes in GERD symptom severity.
- 3) Correlation between absolute changes in high frequency HRV within subjects over the course of the study visit and subsequent changes in GERD symptom severity.

Secondary outcomes:

- 1) The difference in the frequency of supportive provider behaviors between the standard and expanded visit groups.
- 2) The difference in the ratings of rapport, engagement, and reciprocity between the standard and expanded visit groups.

Study population:

Men and women age 21-70 with heartburn symptoms 3 or more days per week. We will enroll until we reach 24 completing subjects.

Study location:

The Clinical Research Center (CRC) at Massachusetts General Hospital (MGH), the Benson-Henry Institute (BHI) for Mind Body Medicine, or another MGH location.

Length of subject participation: 2 weeks

Length of study enrollment: 12-14 months

Groups:

- 1) Standard visit (n=8), modeled after an empathic, high quality conventional primary care visit.
- 2) Expanded visit (n=16), modeled after a visit with an integrative medicine provider

Randomization:

The randomization code will be generated by the study statistician as described below (section 4.3). The study will be single-blinded (study providers and the research team will know what the subject is receiving but the subject will not). Randomization will be

Tool Revision History

Version: 11.0

Version Date: 5.8.2020

stratified based on study provider. We anticipate 4 providers each seeing 6 subjects (2 standard visits, 4 expanded visits).

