9.2 Sample Size and Randomization

This is a pilot study whose aim is to identify features on which to focus in subsequent studies. For the primary outcome, we would consider an observed correlation greater than $r = 0.20$ adequate evidence of a positive association worthy of further investigation. With a sample size of 24 patient-provider dyads, the study will have an 80% probability of obtaining an estimated correlation between physiologic concordance and changes in GERD symptoms (our primary outcome) greater than $r = 0.20$ if the true correlation is at least $\rho = 0.36$. The study will have 80% power to declare the correlation significantly greater than zero based on a two-sided $\alpha = 0.05$ if the true correlation is at least $\rho = 0.54$.

Treatment Assignment Procedures

A randomization scheme will be devised before the start of the study by the study biostatistician who will retain the code and will be responsible for breaking the blind at the end of the study. We do not anticipate a need to break the blind during the study because

Tool Revision History

Version: 11.0

Version Date: 5.8.2020

we are not expecting serious adverse events to occur more frequently in one visit group than another. Randomization will be stratified by provider, with a goal to have 4 providers each see 6 subjects (4 expanded and 2 standard visits each). If a provider cannot commit to this many visits, the study biostatistician may need to adjust the randomization scheme.

The study biostatistician will create numbered envelopes that will indicate which intervention is to be delivered. After a subject has consented to participate in the study, while he or she is completing the baseline questionnaires, immediately prior to the actual visit intervention, the envelope corresponding to the enrolled subject will be opened to reveal which intervention is to be delivered.

If a subject drops or is unable to complete the study, the statistician may need to rebalance the randomization scheme within a stratum.

Subjects will be informed of their “treatment” assignment during a debriefing at the end of the second study visit.

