9.5.1 Primary Outcomes

1. Pearson correlation between concordance in GSR or HRV within patient-provider dyads and improvement in GERD symptom severity in the patient. Changes in GERD symptom severity will be calculated from the GERD symptom diaries collected at the first and second study visits. HRV and GSR will be measured during the visit intervention (first study visit).

We will calculate Pearson correlations between the slopes of time-locked patient and provider GSR data in 15 second intervals after smoothing. An index of concordance in GSR responses for each patient-provider dyad will be calculated as the natural logarithm of the sum of the positive correlations from the entire session minus the natural logarithm of the sum of the absolute value of negative correlations across the session [78]. Dyads with a more positive index demonstrate greater concordance, and the subjects in these dyads would be expected to demonstrate greater improvement in GERD symptom severity.

I will also perform an analysis using a similar approach to analyze the HRV data – comparing variation in the beat-to-beat intervals over short segments of time and calculating Pearson correlation coefficients for time-locked patient and provider data for these intervals.

2. Correlation between change in GSR (or high frequency HRV) and subsequent changes in GERD symptoms. We will calculate absolute changes in GSR, and also for high frequency HRV, within study subjects from the beginning to the end of the study visit and determine the Pearson correlation between these changes and reported changes in GERD symptom severity. As a secondary analysis, I will test whether changes in GSR and HRV are a function of baseline perceived stress and if that relationship differs between the standard and expanded visit interventions.

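### The primary correlations and both 80% figures treat 24 dyads as independent although about four providers supply them; a provider-adjusted correlation should be reported beside the pooled one

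*Combined protocol and SAP*

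**What the plan says.** Section 3 sets the sample by completers ("We will enroll until we reach 24 completing subjects") and the provider structure: "We anticipate 4 providers each seeing 6 subjects (2 standard visits, 4 expanded visits"). Section 9.2 treats four providers as a goal, and Section 4.3 allows for three. Randomisation is stratified by provider.

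Section 9.2 gives the working criterion: "we would consider an observed correlation greater than $r = 0.20$ adequate evidence of a positive association worthy of further investigation". It then attaches 80% to two statements about 24 dyads. The first reads "With a sample size of 24 patient-provider dyads, the study will have an 80% probability of obtaining an estimated correlation between physiologic concordance" and symptom change above r = 0.20, if the true rho is at least 0.36. The second is two-sided 5% significance if rho is 0.54.

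The first primary outcome in Section 9.5.1 is the "Pearson correlation between concordance in GSR or HRV within patient-provider dyads and improvement in GERD symptom severity in the patient". The other two correlate the patient's own change in GSR or high-frequency HRV with symptom change, also by Pearson. Neither section gives a provider term, a provider ICC, a design effect or an independence assumption for these correlations.

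**The concern.** Each provider contributes about six of the 24 points, and the provider's own signal is one of the two series in every concordance index. The protocol's background makes provider effects plausible on both axes. Section 2.1 says that patients of attentive, empathic providers improve more after placebo, and Section 2.2 reports that empathy ratings correlate with synchrony. Provider empathy and personality are measured at enrolment (Section 6.2.2).

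Two things could follow. If both variables cluster by provider, the plain test has more than its nominal error. And if a provider trait raises both synchrony and improvement, pooled r can pass 0.20 with no link from one visit to another within a provider. Section 9.2 says the pilot exists to pick features for later studies, so reading a provider trait as synchrony would misdirect that choice. This bears most on the concordance outcome, since the other two use patient physiology only.

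**Working it through.** **Inputs.** From 9.2: n = 24, threshold r > 0.20, rho = 0.36 and 0.54, two-sided alpha 0.05. From 3, 9.2 and 4.3: 4 providers x 6 subjects, possibly 3 x 8. Provider ICCs are assumed and shown as a range.

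**Step 1: the plan's figures under independence.** Fisher z with standard error 1/sqrt(21):

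- P(r > 0.20 | rho 0.36) = Phi[(0.3769 - 0.2027) x 4.583] = Phi(0.798) = 78.8%. With the bias term rho/(2 x 23) it is 79.8%; by simulation it is 80%.
- Power at rho 0.54 = Phi(0.6042 x 4.583 - 1.960) = Phi(0.809) = 79.1%. With the bias term it is 80.6%; by simulation with critical |r| = 0.404 on 22 df it is 81%.

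Both figures reproduce.

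**Step 2: error of the plain test.** Each variable is simulated as a provider effect plus a dyad effect, with provider effects independent between the two variables. The variance of r under no association grows roughly by 1 + (m - 1) x ICCx x ICCy, with m dyads per provider. At 0.3/0.3 and m = 6 that is 1 + 5 x 0.09 = 1.45. If either ICC is zero it is 1.

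| ICC physiology / symptoms (4 x 6) | Rejection at nominal 5% |
|---|---|
| 0.3 / 0 | 5.0% |
| 0.1 / 0.1 | 5.3% |
| 0.3 / 0.1 | 6.4% |
| 0.3 / 0.3 | 8.9% |

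Repeat runs differ by up to about 0.2 points. With 3 x 8 and 0.3/0.3 the rate is about 10%.

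**Step 3: the 80% figures with clustering, ICC 0.3/0.3.**

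| True structure | P(r > 0.20), rho 0.36 | Power, rho 0.54 |
|---|---|---|
| Independent dyads | 80% | 81% |
| Same rho within and between providers | 77% | 78% |
| rho within provider only, 0 between | 64% | 55% |

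The dyad-level correlation is sqrt(ICCx x ICCy) x rho_between + sqrt((1 - ICCx)(1 - ICCy)) x rho_within. In the last row it is 0.7 x 0.36 = 0.252, or 0.7 x 0.54 = 0.378. Independent dyads at 0.252 pass 0.20 in 61% of trials, so that row's fall in P(r > 0.20) comes mostly from a smaller pooled correlation and not from clustering as such.

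**Step 4: one provider trait drives both variables, no within-provider association.**

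| ICCs | Dyad-level correlation | Pooled r > 0.20 | Adjusted r > 0.20 |
|---|---|---|---|
| 0.1 / 0.1 | sqrt(0.01) = 0.10 | 29% | 19% |
| 0.2 / 0.1 | sqrt(0.02) = 0.14 | 34 to 35% | 19% |

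Under independence with no association at all, pooled r passes 0.20 in 17% of trials.

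**Step 5: the provider-adjusted correlation.** Subtract provider means from both variables and test on n - k - 1 df: 24 - 4 - 1 = 19 (critical r 0.433), or 20 with three providers. Its error is 5.0% in every cell tested. With four providers P(r > 0.20) at within-provider rho 0.36 is 78% and power at 0.54 is 75%; with three they are 79% and 77%. With four providers, 80% is reached at rho of about 0.37 and 0.57.

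**The case against.** A reader might infer that the 80% figures are wrong, or that the error rate and power are simply not as stated. The documents do not support that. The arithmetic is right under independence, no ICC is given, and alpha moves only if both variables cluster. At 0.1/0.1 the shift is negligible. Section 5.1 also describes scripts, instructions to keep empathy equal, provider orientation and feedback from video, all of which could keep provider differences small.

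The large apparent power losses depend on setting the between-provider correlation to zero. With the same rho at both levels they shrink to about 3 points. Likewise, 29 to 35% against 17% is not a false-positive rate for the pooled correlation, because the dyad-level correlation is then truly 0.10 to 0.14. Independent dyads at 0.14 would pass 0.20 in 39% of trials. That is confounding by provider, not a miscalculated error.

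Nor is stratification the cause. The primary estimand is a correlation, not a contrast between arms; what matters is that dyads share providers.

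Finally, replacing the pooled coefficient would change the question. Hypothesis 1 in Section 9.1 compares dyads of higher and lower concordance in general. If some providers synchronise better and their patients improve more, that may be mechanism, and centring deletes it. With between-provider rho 0.8, within-provider rho 0.16 and ICC 0.3/0.3, the chance of r > 0.20 falls from 69% pooled to 44% adjusted.

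All of this stands. It limits the size of the point and rules out making the adjusted coefficient the sole primary one. It leaves untouched that pooled r cannot distinguish a provider trait from dyad-level synchrony, and that the plan states no independence assumption.

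**Conclusion.** The point holds in a conditional form. The primary correlations and both 80% figures rest on an unstated assumption of independent dyads. If provider effects are small, or present in only one variable, the 5% error rate is close to nominal. If both ICCs are near 0.3, the 5% test runs at about 9%, and the 80% figures become 77% and 78% with a common rho, or 64% and 55% if the association is within provider only. These ICCs are assumptions.

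The firmer part is interpretive: a shared provider trait at modest ICCs passes the go criterion in 29 to 35% of trials without any within-provider link, and the planned analysis would not show it. In a pilot meant to choose features for later work, that merits a change to the plan. It is not evidence that the sample size calculation is in error.

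**What to change.** In Section 9.5.1, keep the pooled Pearson r and pre-specify beside it the provider-adjusted (within-provider) correlation: subtract provider means from both variables, or correlate residuals from models with provider as a factor. Test it on n - k - 1 df, where k is the number of providers (19 with four, 20 with three). Describe an association as dyad-level only if the adjusted r also exceeds 0.20.

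In Section 9.2, state that rho = 0.36 and 0.54 assume independent dyads, and give the provider-adjusted values of about 0.37 and 0.57 for four providers.

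No new data are needed. The adjusted coefficient costs three degrees of freedom with four providers (22 to 19): 78% instead of 80% for r > 0.20 at rho 0.36, and 75% instead of 81% power at 0.54. Under no association it also passes 0.20 slightly more often, 19% against 17%. It removes any genuine between-provider association, which is why the pooled r stays.

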9.3 Definition of Populations

For analyses including intervention group, we will analyze our data according to which visit intervention subjects received (standard or expanded). We do not anticipate any discrepancies between what subjects were assigned to receive by randomization and what they actually received. Study visit type will be guided by a written script that the providers will follow during the visit. The actual intervention received will also be verified by reviewing study video recordings.

9.4 Interim Analyses and Stopping Rules

As this is a pilot study, the study PI will review video recordings of visit interventions as the study progresses to offer feedback to the study intervention providers. To ensure that we will have an adequate response rate to analyze our outcomes of interest, we will analyze changes in GERD symptom improvement after 6 subjects have completed the expanded visit intervention (we will not break the blind for unenrolled subjects). If there are not at least 2 subjects with a 50% or greater improvement in GERD symptoms and it is deemed that the study providers are delivering the standard and expanded interventions appropriately, we may consider protocol amendments to improve subject expectancy for symptom improvement.

9.5 Outcomes

Tool Revision History

Version: 11.0

Version Date: 5.8.2020

Assessment	Time Points Collected	Analysis Plan	Section
Demographics, health behaviors, height & weight	Visit 1	Descriptive statistics	9.6
Daily GERD Symptom Diary	Visit 1 & Visit 2	Primary Outcome - Pearson correlation between change in GERD symptom severity and physiologic concordance in patient-provider dyads	9.5.1
GERD-HRQL	Visit 1 & Visit 2	Descriptive statistics and secondary measures of GERD symptom severity	9.6
NIH PROMIS GERD			
GSRS			
Current Stress	Visit 1 (both before & after provider visit) & Visit 2		9.6
PSS-10	Visit 1 (before provider visit) & Visit 2	Generalized linear model to determine whether perceived stress is a modifying factor for change in GSR and HRV in the context of the visit intervention	9.6
FFI	Visit 1	Generalized linear model to determine whether personality is a modifying factor for change in GERD symptoms in the context of the visit intervention	9.6
GSR & HRV	Visit 1	Primary Outcome - Pearson correlation between change in GERD symptom severity and physiologic concordance in patient-provider dyads	9.5.1
Video Recording	Visit 1	Secondary Outcomes - generalized linear mixed models to compare the frequency of supportive provider behaviors and ratings of rapport, engagement, and reciprocity between the standard and expanded visit groups.	9.5.2
CARE	Visit 1, post-intervention	Generalized linear model to determine whether empathy and the patient-provider connection modify change in GERD symptoms in the context of the visit intervention	9.6
HEAL Patient-Provider Connection			
Qualitative Interview	Visit 2	Qualitative analysis to understand subjects' experiences of the study and with healthcare providers generally	9.6

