Subjects will have a single visit with a “study provider,” a physician or nurse practitioner who they have never previously met. Subjects will complete a daily symptom diary for 2 weeks following this visit and return for a second study-related visit in which they will complete questionnaires and be debriefed by a physician on the study team (not the individual who conducted the study intervention visit).

Sample Size and Population

We plan to enroll to obtain 24 completing subjects with GERD, age 21-70 with heartburn symptoms 3 or more days per week. To permit a spread of physiologic, behavioral, and symptom responses, 16 subjects will be randomized to the expanded visit intervention and 8 subjects will be randomized to the standard visit intervention (2:1 expanded:standard

Tool Revision History

Version: 11.0

Version Date: 5.8.2020

randomization). We will stratify randomization by study provider such that each provider will see 6 subjects (4 expanded visits and 2 standard visits).

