2.2 Study Rationale

Recent studies are beginning to reveal the neural correlates of empathy, both in general [36] and in patient-provider relationships [37,38]. Activation of specific neural pathways drives changes in autonomic nervous system regulation [39], resulting in downstream changes in physiologic

biomarkers such as galvanic skin response (GSR) and heart rate variability (HRV) [40,41]. A growing body of research has identified concordance in physiologic biomarkers between individuals. An excellent review of this topic, also known as “interpersonal autonomic

Figure 1: Proposed model for mechanisms underlying the patient-provider relationship

Tool Revision History

Version: 11.0

Version Date: 5.8.2020

physiology” or “physiologic synchrony,” has recently been published [42]. The authors reviewed 61 studies covering relationships between therapist and client, couples, mother and child, teammates, and other relationships. There were 8 studies of the therapist-client relationship which examined either heart rate (HR) or skin conductance/galvanic skin response (GSR). Multiple studies found positive correlations between empathy ratings and physiologic synchrony. The study I have proposed would be the first to examine physiologic biomarkers in the context of physician-patient interactions in a medical setting.

As illustrated in Figure 1 above, we hypothesize that moment-to-moment autonomic changes in patients and providers over the course of a visit collectively influence perceptions of the encounter (part of the “neural response”) and response to treatment and that improved treatment response is associated with increased concordance in these autonomic changes.

GSR and HRV can also be used to assess relative physiologic stress vs. relaxation [43]. Typically GSR and HR decrease and high frequency HRV increases in the relaxed state [24,44,45]. While empathic visits may theoretically reduce patients’ allostatic load and distress [46], this hypothesis has not been studied rigorously. Newer computational approaches incorporating complexity theory to the analysis of physiologic data [47] have yielded valuable insights to the study of human disease (e.g., decreased HRV is associated with increased cardiovascular mortality [48,49]) and the effects of integrative modalities such as tai chi [50,51]. There is limited data using these approaches to study client-therapist interactions [52–54].

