6.2.4 Post Intervention Measures (Day 0)

Immediately following the study physician visit, subjects who consented to blood draws will be asked to have another 7.5mL sample of blood taken (to obtain RNA and plasma) and all subjects will be asked to complete the following questionnaires:

- CARE – Consultation And Relational Empathy questionnaire, a validated and commonly used 10 item measure for assessing the quality of the patient encounter and perceptions of empathy from the treatment provider [76]. I used it in my pilot study.
- HEAL Patient-Provider Connection – a subset of the Healing Encounters and Attitudes List, a recently validated 7-item measure of the patient-provider connection. This is a patient-reported outcome developed as part of a set of tools to measure non-specific factors in treatment using the NIH PROMIS methodology [77].
- Current Stress Question – 1 item self-report measure of current stress level on a scale of 0 (no stress) to 10 (extreme stress).

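### CARE and HEAL are measured after the randomised visit and can be changed by it, so they should be analysed as exploratory post-visit correlates or possible mediators, not alongside baseline traits as modifiers

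*Combined protocol and SAP*

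**What the plan says.** **Timing.** Section 6.2.4 places CARE and HEAL here: "Immediately following the study physician visit". The schedule in section 6.1 and the table in section 9.5 agree. Section 6.2.2 places randomisation just before the visit, so both scores are post-randomisation.

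**Planned analysis.** The section 9.5 table gives one entry for the two scores: "Generalized linear model to determine whether empathy and the patient-provider connection modify change in GERD symptoms in the context of the visit intervention". Section 9.6 repeats the modifier framing and puts perceived empathy in the same sentence as perceived stress and personality type. Neither section lists the model terms. No comparison of CARE or HEAL between arms and no mediation analysis is planned anywhere.

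**Role in the rationale.** Section 2.1 offers increased perceived empathy or trust as one of several explanations for the effect of an integrative consultation. Section 2.2 hypothesises that "moment-to-moment autonomic changes in patients and providers over the course of a visit collectively influence perceptions of the encounter", and also response to treatment.

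**Countervailing text.** Section 5.1 instructs providers to be equally empathic in both arms. Section 9.6 admits that these analyses may be underpowered.

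**The concern.** A modifier is normally a characteristic that exists before treatment and changes how well treatment works. A score that the treatment can itself alter may instead lie on the path from treatment to outcome. Asking whether the arm effect differs by level of such a score conditions on a consequence of randomisation, and it is a different question from whether the score carries the effect.

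The stake is modest but real. Section 9.2 says the pilot is meant to pick out features for later studies. If perceived empathy did transmit part of the visit effect, a null interaction could lead the team to drop it for no good reason.

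**Working it through.** **1. The plan's own figures.** No figure is given for CARE or HEAL. The only power statements, in section 9.2, are for the primary correlation ("With a sample size of 24 patient-provider dyads"), and they reproduce. With Fisher's z, SE = 1/√(24 − 3) = 0.218.
- P(r > 0.20 when ρ = 0.36) = Φ[(0.377 − 0.203)/0.218] = 78.8%; by simulation 80.1%.
- Power at ρ = 0.54 = Φ[0.604/0.218 − 1.96] = 79.1%; by simulation 80.8%.

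Both agree with the stated 80%, so the sample-size section is not in question.

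**2. Is an interaction meant?** Set two entries side by side. The section 9.5 table describes the PSS-10 analysis with the same closing phrase about the visit intervention as the CARE/HEAL entry. Section 9.5.1 then spells out the PSS-10 analysis as including whether the relationship differs between the two visit types, which is a group-by-score interaction. That supports reading the CARE/HEAL model the same way, but it remains an inference.

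**3. What such a model would show under mediation.** The arm sizes come from the Précis: "16 subjects will be randomized to the expanded visit intervention and 8 subjects will be randomized to the standard visit intervention". The documents give no effect sizes for CARE or HEAL, so these are assumptions:
- score M = a × arm + error with SD 1, with a = 0, 0.5 or 1 SD;
- symptom improvement Y = b × M + error with SD s, with b = 0.5 or 0.6, and s = 1 or √(1 − b²) (0.87 and 0.80);
- no direct arm effect and no true interaction.

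Each of the 12 combinations was simulated 20,000 times, with two-sided tests at 0.05. Ranges run over b and s.

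| Arm shift in score (a) | Arm × M significant | M significant, interaction in model (standard arm as reference) | M significant, adjusted for arm, no interaction | Arm effect on M significant | Arm effect on M and M given arm both significant |
|---|---|---|---|---|---|
| 0 | 5% | 24–46% | 59–89% | 5% | 3–4% |
| 0.5 SD | 5% | 24–45% | 59–89% | 20% | 10–17% |
| 1 SD | 5% | 24–44% | 59–89% | 60% | 35–52% |

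Other runs of the same set-up differed by no more than about two points (for example, an upper value of 54% instead of 52%).

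**4. Why the CARE coefficient weakens.** With the interaction included and the standard arm as reference, the CARE coefficient is the slope among 8 subjects, with an expected within-arm sum of squares of 7 units. Without the interaction it uses 7 + 15 = 22 units. The standard error is therefore larger by about √(22/7) = 1.77.

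**5. Precision of the arm difference.** SE = √(1/16 + 1/8) = 0.433 SD. The 95% half-width is 2.074 × 0.433 = 0.90 SD. This is wide, so estimation is the realistic aim.

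**The case against.** **The terms are inferred.** Section 9.5.2 names its interaction outright, and the CARE/HEAL entry does not. The section 9.6 wording could mean a regression of symptom change on the score, with or without arm. That stands as a limit on the claim: such a model would show a CARE association, and the 5% figure applies only to the interaction.

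**A reader might infer that the plan would miss the mechanism the study is looking for.** The documents do not support this. The primary hypotheses (section 9.1) concern GSR and HRV and have their own correlations (section 9.5.1). The secondary hypothesis uses coded video and mixed models (section 9.5.2). CARE and HEAL belong to the exploratory analyses of section 9.6.

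**A reader might also take 59–89% as the power to detect mediation.** It is not. The first row of the table shows the same rate when the visit does not shift the score at all. Nor would an arm effect near zero given CARE, next to a clear CARE association, count against mediation; that pattern is what full mediation produces.

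**The causal path is not fixed by the text.** Section 2.2 can be read as making perceptions and treatment response parallel effects, and Figure 1 is not available here. The equal-empathy instruction may also keep the arm difference in CARE small. Both points stand. Neither turns a post-visit score into a baseline modifier, and the instruction is itself a reason to report CARE by arm.

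**Conclusion.** The point holds in a limited form. CARE and HEAL are post-randomisation scores that the visit can change, and perceived empathy is one mechanism the protocol itself names, yet they are grouped with baseline traits as modifiers. If the model contains a group-by-score interaction, as the PSS-10 parallel suggests, that term says nothing about a mediated effect: it is significant about 5% of the time under assumed full mediation. It also lowers detection of the CARE term from about 59–89% to 24–46%. These figures rest on assumed effects, linear relations and normal errors. The criticism does not touch the primary or secondary analyses, or modifier models for measures taken before the visit. It is a minor improvement to an exploratory analysis.

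**What to change.** In sections 9.5 and 9.6, replace the modifier model for CARE and HEAL with two exploratory analyses and list their terms:

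- (a) the difference in CARE and in HEAL between arms, which also checks whether the equal-empathy instruction in section 5.1 held;
- (b) the association of each score with change in GERD severity, adjusted for arm, with further adjustment for provider and baseline severity as a sensitivity analysis.

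Report both as estimates with confidence intervals. Keep modifier models for measures taken before the visit: baseline PSS-10, NEO-FFI and the provider IRI.

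The cost is a few lines of text, with the same data and software. The limits should be written in. CARE and HEAL are not randomised, so (b) is open to confounding and shows association, not proof of mediation. With 24 completers a joint mediation test has low power, as the table shows, and a non-significant result should not be used to rule perceived empathy out.
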